11.3.2 Secondary Endpoint

The secondary endpoints are:

- Maximum SOFA score: Maximum SOFA score over 7 days.
- Mean SOFA Score (Days 2-5).
- Prolonged organ failure: Defined as SOFA>5 on Day 7.
- Days on organ support: As per the CTCOFR score (Nadel *et al.*, 2007).
- Incidence of acute lung injury: As per Berlin definition (ARDS Task Force, 2012).
- Incidence of acute kidney injury: As per the RIFLE score (Bellomo *et al.*, 2004).
- Incidence of infection: As per definitions of infection by (Cole *et al.*, 2014).
- Number of ventilation free days.
- Total length of hospital stay.
- Total length of critical care stay.
- Mortality (discharge, 28 day and 90 day).
- Alive and free of multiple organ failure (defined as SOFA <=>) at 48 hours.

The safety endpoint is the serious adverse event rate in the first 28 days.

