17.4 Notification and reporting Adverse Events or Reactions

If the AE is not defined as SERIOUS, the AE is recorded in the study file and the participant is followed-up by the research team.

Death as a result of disease progression and other events that are primary or secondary outcome measures are often not considered to be SAEs and can be reported in the normal way on the CRF.

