17.6 Adverse events that do not require reporting

The period for AE reporting is from dose administration to 28 days. The following SAEs are clinical outcome measures and are expected due to the nature of the injuries sustained:

- Deaths
- Infection
- Organ failure (single or multi-)
- Acute lung injury
- Acute kidney injury

The following SAEs are not clinical outcome measures but are expected SAEs due to the nature of injuries sustained:

- Thromboembolic events (deep vein thrombosis, pulmonary embolism)
- Ischaemic events (myocardial infarction, stroke, transient ischaemic attack)
- New-onset major bleeding

New onset major bleeding refers to a second episode of major bleeding which is temporally and clinically separate from the major haemorrhage that led to the entry of the participant into this study.

Any event meeting the definition of an SAE and not listed above will be treated as an 'unexpected SAE' and will require notification as outlined in Section 17.7.

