17.7 Notification and Reporting of Serious Adverse Events & SUSARs

All Serious Adverse Event (SAEs) will be recorded in the participants' notes, the CRF, electronic database, the sponsor SAE form and reported to the sponsor (Joint Research Management Office)/IMP provider (as per IMP supply agreement) within 24 hours of the PI or co-investigators becoming aware of the event (excepting those specified in this protocol – Section 17.6, as not requiring reporting). Nominated co-investigators will be authorised to sign the SAE forms in the absence of the PI at the participating site.

Suspected Unexpected Serious Adverse Reactions (SUSARs) that occur during the trial will be reported to the JRMO/IMP provider (as applicable IMP supply agreement) within 24 hours of the PI or co-investigator becoming aware of the event. SUSARs should be reported to the sponsor (JRMO) within 24 hours.

If the AE is not defined as SERIOUS, the AE is recorded in the study file and the research team will follow up the subject.

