28.0 Trial Committees

Trial Management Group

A Trial Management Group (TMG) comprising the Chief Investigator, Clinical Trials Coordinator and lead Clinical Research Fellow will be responsible for the day-to-day running and management of the trial. The Trial Management Group (TMG) will meet regularly to ensure all practical details of the trial are progressing and working well and everyone within the trial understands them.

Trial Steering Committee

The role of the Trial Steering Committee (TSC) is to provide overall supervision for the trial and provide advice through its independent chairperson. In accordance with the Trial Terms of Reference for the TSC, the TSC is responsible for periodically reviewing safety data and liaising with the DMC regarding safety issues. The ultimate decision on continuation or discontinuation of the trial lies with the TSC.

Members of the TSC will include membership from the TMG and independent members including:

Independent Chair Independent Lead Clinical Experts Lay-person/Patient Representative Clinical Trial Coordinator Co-optable Members including the trial chief investigator, trial statistician and trial collaborators

Data Monitoring (and ethics) Committee

In accordance with the Trial Terms of Reference for the DMC, the DMC are responsible for periodically reviewing un-blinded overall safety data to determine patterns and trends of events, or to identify safety issues, which would not be apparent on an individual case basis. The Regulations require that all Serious Adverse Events (SAEs), unless excluded in the protocol are reviewed by an appropriate Safety Monitoring Committee.

Members of the DMC will be completely independent from the running of the trial. For the purposes of this study, an independent member who can provide expert disease specific advice will join the core DMC.

The group will be called at the interim review for a formal analysis of safety data as outlined in Section 19 of this protocol. The TSG may also request further reviews by the DMC regarding any safety concerns or issues regarding trial management arising outside of the interim review period. The DMC may also provide advice to the Chair of the TSC and can recommend premature closure of the trial.

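### Read literally, Sections 17.4, 17.6 and 17.7 except eight classes of SAE from recording and reporting, although the only safety endpoint is the 28-day SAE rate; Sections 13.8 and 19.9 point the other way

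*Protocol*

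**What the plan says.** Section 11.3.2 defines safety in one line: "The safety endpoint is the serious adverse event rate in the first 28 days". The table in Section 11.5 repeats it and names no other safety endpoint.

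Section 17 then sets events aside:

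- The heading of 17.6 reads "17.6 Adverse events that do not require reporting". Its first list (deaths, infection, single or multiple organ failure, acute lung injury, acute kidney injury) opens with "The following SAEs are clinical outcome measures and are expected due to the nature of the injuries sustained".
- Its second list (thromboembolic events, ischaemic events, new-onset major bleeding) opens with "The following SAEs are not clinical outcome measures but are expected SAEs due to the nature of injuries sustained".
- Section 17.7 requires SAEs to be entered in the notes, CRF, database and sponsor form and reported within 24 hours, "excepting those specified in this protocol – Section 17.6, as not requiring reporting".
- Section 17.4 adds: "Death as a result of disease progression and other events that are primary or secondary outcome measures are often not considered to be SAEs". It allows such events to go on the CRF in the ordinary way.

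Section 28.0 describes the regulatory requirement as being that "all Serious Adverse Events (SAEs), unless excluded in the protocol are reviewed by an appropriate Safety Monitoring Committee".

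Section 19.9 confines the interim, after 52 patients, to safety data. The DMC makes a qualitative assessment of all recorded AEs and SAEs, and an overview by group includes AEs leading to withdrawal or death. The DMC is to define the termination criteria, with total SAEs per group as the example. Section 13.8.1 calls for SAEs to be recorded through day 28.

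**The concern.** An SAE rate means something only if it is clear which SAEs enter it. In this population the listed classes are the serious events most to be expected. If they are left out, the safety endpoint compares only the remainder. An excess of deaths, clots or re-bleeds on artesunate would not move it, and neither would a reduction.

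The interim raises the stakes. Sections 9.1, 11.6 and 19.9 make the step from 2.4 to 4.8 mg/kg depend on that safety review alone. If total SAEs per group is computed without the listed classes, the decision rests on a count from which the commonest serious harms have been removed by rule.

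**Working it through.** There is no stated figure to reproduce. The check compares the text of the sections and then gauges scale.

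**Step 1: how far the exception reaches.** In Section 17.7 one sentence carries notes, CRF, database, sponsor form and 24-hour reporting, and the words "excepting those specified in this protocol" qualify that sentence. Taken literally, the exception removes recording as an SAE as well as rapid notification. For outcome events, 17.4 adds that they are often not SAEs at all; an event that is not an SAE cannot enter an SAE rate.

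**Step 2: what catches each class elsewhere.**

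| Class in 17.6 | Endpoint in 11.3.2 | Own row in the 13.8.2 schedule |
|---|---|---|
| Deaths | Mortality | Yes |
| Infection | Incidence of infection | Yes |
| Organ failure | SOFA and CTCOFR measures | Yes |
| Acute lung injury | Incidence | Yes |
| Acute kidney injury | Incidence | Yes |
| Thromboembolic events | None | No |
| Ischaemic events | None | No |
| New-onset major bleeding | None | No |

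The first five are kept as secondary efficacy endpoints, but an interim limited to safety data need not tabulate those. The last three have only the general AE and SAE rows, which the exception puts in doubt. The CRF route in 17.4 covers deaths from disease progression and outcome events, so it does not reach them. Section 17.5 names no events of special interest. Appendix 3 covers thromboembolic and ischaemic events, and 17.6 itself defines new major bleeding, but nothing says where any of them is counted.

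**Step 3: what points the other way.** Section 17.6 still calls all eight classes SAEs. Section 13.8.1 has SAEs recorded without exception. Section 19.9 gives the DMC everything recorded. No section says whether a listed event counts in the 28-day rate or must be shown to the DMC.

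**Step 4: scale at the interim.** Inputs: 35 low-dose and 17 placebo patients (Section 11.6). From Section 9.1: 30% multiple organ failure in the severely injured; mortality of 35% in patients needing at least four red-cell units, against 6% in the comparison group. Assumption: each rate applies equally to both arms. Expected count = n × rate.

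| Event and rate | Low dose, n = 35 | Placebo, n = 17 | Total, n = 52 |
|---|---|---|---|
| Deaths, 6% | 35 × 0.06 = 2.1 | 17 × 0.06 = 1.0 | 3.1 |
| Deaths, 35% | 35 × 0.35 = 12.3 | 17 × 0.35 = 6.0 | 18.2 |
| Multiple organ failure, 30% | 35 × 0.30 = 10.5 | 17 × 0.30 = 5.1 | 15.6 |

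The rows overlap, because a patient may have organ failure and die, so they must not be added. The protocol gives no rates for thromboembolism, ischaemia or re-bleeding, and none for infection, lung injury or kidney injury.

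**The case against.** The strongest defence is that 17.6 exempts events from notification only. It never says that they go unrecorded. Its closing sentence contrasts them with events that need notification, and the parenthesis in 17.7 follows the 24-hour clause and speaks of reporting. The literal reading would even keep deaths out of the patient's notes, which nobody can intend. Sparing expected outcome events from expedited reporting is a legitimate choice here. This shows that the narrow reading is plausible, but not that the text settles it: the exception is attached to the recording sentence, and 17.4 removes outcome events by a separate route.

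Three stronger inferences are tempting, and the documents do not support them.

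- **That the interim will in fact miss the main harms.** Section 19.9 shows AEs leading to death by group, as well as abnormal laboratory values, and the safety bloods include creatinine, bilirubin and platelets. Section 28.0 states what regulations require, and the sentence before it gives the DMC overall unblinded safety data. It sets a minimum and does not limit what the DMC may see.
- **That a listed event related to artesunate escapes SUSAR handling.** The SUSAR paragraph of 17.7 has no exception, 17.2 requires causality to be assessed for all serious events and expectedness for all SARs, and 17.1 ties expectedness to the Reference Safety Information. What remains is a wording problem: 17.6 uses expected in another sense, based on the injury.
- **That 35% mortality describes this trial.** It belongs to patients needing at least four red-cell units. That is not an entry criterion, and patients not expected to survive 48 hours are excluded. Hence the range down to 6%.

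The SAP or the DMC charter may say what is tabulated. Neither should have to override a protocol exception attached to the recording of SAEs.

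**Conclusion.** The point holds as a conflict within the protocol. On the literal wording of 17.4, 17.6 and 17.7, eight classes of serious event are excepted from SAE recording and reporting, and so from the only safety endpoint and from the example stopping count. Sections 13.8 and 19.9 indicate that they are recorded and seen. A sole safety endpoint and the review that precedes a dose increase should not be open to two readings this far apart.

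The gap is most serious for thromboembolic events, ischaemic events and new major bleeding, because no endpoint or dedicated schedule row would recover them. For deaths and organ outcomes, the final secondary analyses give partial cover.

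The events in doubt at the interim are about 2 to 12 deaths on low dose and 1 to 6 on placebo, and about 10 and 5 multiple organ failures. These counts assume that the background rates carry over and are equal in both arms. They show how much of the safety comparison is unsettled and do not predict a difference between arms.

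**What to change.** Reconcile Sections 11.3, 17.4, 17.6, 17.7, 19.9 and 28.0 before the interim, by stating that:

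1. the 17.6 exemption concerns expedited notification to the sponsor only, and only for listed events judged unrelated to the IMP;
2. every listed event is recorded on the CRF;
3. listed events count in the 28-day SAE rate, which is shown overall and with the listed classes separately;
4. deaths and each listed class are tabulated by arm for the DMC at the interim;
5. the 17.6 list does not determine the expectedness of a related event, which is judged against the Reference Safety Information as in 17.1.

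The cost is wording in six sections and a few CRF lines; Appendix 3 and 17.6 already supply definitions for the three classes without an endpoint. The reported SAE rate will be higher and will partly overlap the secondary endpoints. Showing the listed classes separately lets a reader see the rate with and without them.

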17.7 Notification and Reporting of Serious Adverse Events & SUSARs

All Serious Adverse Event (SAEs) will be recorded in the participants' notes, the CRF, electronic database, the sponsor SAE form and reported to the sponsor (Joint Research Management Office)/IMP provider (as per IMP supply agreement) within 24 hours of the PI or co-investigators becoming aware of the event (excepting those specified in this protocol – Section 17.6, as not requiring reporting). Nominated co-investigators will be authorised to sign the SAE forms in the absence of the PI at the participating site.

Suspected Unexpected Serious Adverse Reactions (SUSARs) that occur during the trial will be reported to the JRMO/IMP provider (as applicable IMP supply agreement) within 24 hours of the PI or co-investigator becoming aware of the event. SUSARs should be reported to the sponsor (JRMO) within 24 hours.

If the AE is not defined as SERIOUS, the AE is recorded in the study file and the research team will follow up the subject.

17.8 Sponsor Medical Assessment

Sponsor has delegated the responsibility for oversight of IMP safety profile and medical assessment of SAEs and SUSARs to the CI. The CI must review all SAEs within 24 hours of receipt. This review should encompass seriousness, relatedness and expectedness. Day 0 for all SUSARs is when the SAE/SUSAR is received by the CI and /or coordinating team and /or sponsor whichever is first.

It is expected that the CI will achieve oversight of IMP safety profile through trial committees as per section 28.0.

It is noted that the CI can upgrade an event to 'related' or 'unexpected' but cannot downgrade the PI or delegate assessment of an event to 'unrelated' or 'expected'. If there is disagreement between CI and PI (or delegate) assessment, it is the CI's responsibility to liaise with the Site PI or delegate before CI's final decisions. The CI and PI/delegate assessment can differ.

17.9 Urgent Safety Measures

The CI may take urgent safety measures to ensure the safety and protection of the clinical trial subjects from any immediate hazard to their health and safety, in accordance with Regulation 30. The measures should be taken immediately. In this instance, the approval of the Competent Authority prior to implementing these safety measures is not required. However, it is the responsibility of the CI to attempt, where possible, to discuss the proposed changed with the Sponsor and Medical Advisor at the MHRA (via telephone) prior to implementing the change if possible.

The CI has an obligation to inform both the MHRA and Research Ethics Committee **in writing within 3 days**, in the form of a substantial amendment. The sponsor (JRMO) must be sent a copy of the correspondence with regards to this matter as soon as it is sent.

17.10 Procedures for reporting blinded SUSARs

The CI as sponsor medical assessor will assess the event blinded for all possible IMPs/combinations.

17.11 Pregnancy

If a patient becomes pregnant whilst involved in a CTIMP, it is not considered to be an SAE or an AE. However, it is an event that requires reporting, monitoring and follow up. If a participant, or participant's partner, becomes pregnant whilst or after taking an IMP the sponsor should be notified immediately (within 24 hours of site becoming aware of the pregnancy) using the sponsor pregnancy form. The pregnancy reporting procedure will be the same as the SAE reporting route.

The CI in conjunction with the site PI/delegate should determine if the foetus has been exposed to an investigational medicinal product. The PI has the responsibility to ensure that the pregnancy form is completed and sent to the sponsor within the agreed timelines. The initial report should be sent within 24 hours and follow up information submitted as and when it becomes available up to agreed follow up time after birth.

Participants are screened for pregnancy prior to enrolment in the trial (and administration of the single IMP bolus dose) and excluded in the event they are pregnant. If a participant subsequently becomes pregnant whilst enrolled in the trial they are they can continue on the study for follow-up assessment and monitoring. The manufacturer will be informed.

Wherever possible, any pregnancy will be followed to term, any premature termination reported, and the status of the mother and child will be reported to the sponsor after delivery. Any events to the mother or child that occur during this time that could be considered to be a SAE must be reported to the sponsor in line with section 17.7, utilising the sponsor SAE reporting form.

18.0 Annual reporting

Development Annual Safety Update (DSUR)

The DSUR will be written by the CI (using Sponsor template) and submitted to the sponsor for review prior to submission to the MHRA. The DSUR is due for submission within 60 days of the end of the reporting period. The reporting period is annually from the date on the "notice of acceptance letter" from the MHRA. As delegated Sponsor Medical Assessor the CI will carry out a risk benefit analysis of the IMPs encompassing all events having arisen on the trial. REC will be sent a copy of the DSUR.

Annual Progress Report (APR)

The APR will be written by the CI (using HRA template) and submitted to the sponsor for review prior to submission to the REC. The APR is due within 30 days of the anniversary date of the "favourable opinion" letter from the REC.

19.0 Statistical and Data Analysis

19.1 Sample size calculation

The primary objective of this trial is to determine the signs of potential efficacy of Artesunate in reducing multiple organ failures and complications. To establish this, the primary comparison of interest will be on the SOFA score at 48 hours.

Each of the Artesunate dose level groups will be compared to placebo. For each dose level the null hypothesis will be that there is no difference in the response rates between Artesunate and placebo, the alternative hypothesis being that the response rate is higher for Artesunate than for placebo.

This is a Phase 2a study and we are looking for safety and efficacy data with which to appropriately power a subsequent definitive 2b trial. A formal sample size calculation is not possible given the lack of existing human efficacy data.

However if Artesunate leads to a clinically relevant 2-point reduction in 48-hour SOFA score, this study will have a power of 80% to detect this difference with 70 intervention and 35 control subjects (α =0.05; σ =3.43) by unpaired t-test.

The intervention arms will consist of 35 subjects receiving Artesunate at 2.4 mg/kg and 35 receiving Artesunate at 4.8 mg/kg. We shall also perform two one-sided t-tests on each of the two intervention arm does levels against the placebo where 35 patients in each arm will detect a 2-point reduction in 48-hour SOFA (α =0.05; σ =3.43) with 78% power.

This should provide enough data on safety profile and potential clinical efficacy to determine whether progression to a 2b study is justified and to develop an appropriate study protocol.

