5.0 Trial Summary

Full title	A randomised, blinded placebo-controlled phase 2a study to evaluate the safety and efficacy of Artesunate treatment in severely injured trauma patients with traumatic haemorrhage.
Short title and/or Acronym	TOP-ART
Trial Design Methodology	Randomised, blinded placebo-controlled, parallel group study.
Phase of the Trial	Phase 2a
Study Duration	27-months.
Study setting	Single-site NHS Major Trauma Centre
Investigational Medicinal Product(s) and Treatment Groups	 IMP: Artesunate provided as a white crystalline powder in a glass vial containing 110mg, supplied with a second glass vial of reconstitution diluent which is a sterile phosphate buffer comprised of a mixture of sodium phosphate monobasic monohydrate, sodium phosphate dibasic anhydrous and water for injection to achieve a 0.3 M solution with a pH of 8.0 (7.9-8.1). Matching placebo will comprise of the same, buffered diluent drawn up to the volume that would be necessary to reconstitute active IMP according to the subjects' weight. The sterile phosphate buffer is provided in a glass vial and is comprised of a mixture of sodium phosphate monobasic monohydrate, sodium phosphate dibasic anhydrous and water for injection to achieve a 0.3 M solution with a pH of 8.0 (7.9-8.1). Treatment group 1 (low dose intervention group): Subjects will be dosed at 2.4 mg/kg. Treatment Group 2 (high dose intervention group): Subjects will be dosed at 4.8 mg/kg. Control Group: Subjects will be receiving placebo at the same dose as treatment groups 1 or 2 respectively
Medical condition or disease under	Trauma haemorrhage
Planned Sample Size	105
(Maximum) Treatment duration	1-2 minutes (time taken to administer bolus injection of IMP or comparator)
Follow up duration	90 Days
End of Trial definition	Point at which all surviving Subjects have completed 90-day mortality check.

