9.3 Rationale for study design

This study aims to investigate whether administration of a single intravenous bolus dose of Artesunate reduces multiple organ failure in severely injured patients with trauma haemorrhage. The rationale for the study include:

- 1. Pre-clinical data provide both clinical and mechanistic evidence of the potential benefit of Artesunate in reducing multiple organ failure.
- 2. There are currently no other specific therapeutic agents that are proven to effectively attenuate multiple organ failure and its detrimental consequences in human studies (Lord et al., 2014)
- 3. Artesunate has a well-documented favourable safety profile, including in other critical illnesses.

The patient will receive the usual standard of care regardless of whether or not they receive Artesunate. With regards to dosage, 2.4mg/kg as a bolus is the recommended treatment does for malaria (a bolus which is repeated 12 hours later). There is published safety data for Artesunate using intravenous boluses up to 8mg/kg (Li *et al.* 2009, Miller *et al.* 2012).

In our study, due to the dose-dependent benefit seen in the pre-clinical data, we wish to determine whether an increased dose of 4.8mg/kg Artesunate is more efficacious than 2.4mg/kg in reducing multiple organ failure following major haemorrhage in trauma. We do not expect a significant increase in serious adverse events in relation to this increased dose, although this will be closely monitored.

A placebo is justified in this trial to reduce effects of potential investigator bias when collecting follow-up data (including on organ failure) and potential bias arising from differential treatment by clinicians on account of knowing the patient's enrolment in the trial.

Please see section 9.2 for further assessment of the risks and benefits of the study.

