11.6 Trial Design

This is a single-centre, randomized, placebo-controlled, parallel group study with a sequential groupdosing regimen (adaptive design). Its aim is to evaluate the safety and efficacy of Artesunate treatment compared to placebo, in addition to standard treatment, in severely injured trauma patients with traumatic hemorrhage. All subjects will be managed in accordance with local guidelines for traumatic hemorrhage.

Subjects will be assessed for eligibility upon arrival to the hospital. Due to the urgent/emergency nature of the intervention subjects will be recruited within 4 hours of their injury and within 2 hours of admission to the accident and emergency department. Eligible patients therefore need to be consented very soon after admission. As most, but potentially not all, subjects will be incapacitated at time of eligibility, consent can be obtained from relatives or if no relatives are present two

doctors (one independent of the trial) will decide on consent. If and when the subject regains physical and mental capacity they will be provided written information on the trial and will be given the opportunity to ask questions, informed consent will be sought for continuation in the trial. For any subject included but did not regain full capacity, consent will be sought from a relative or other appropriate representative for continuation in the trial.

Subjects will be randomized to one of three groups:

- Placebo arm (n = 35)
- Low Dose intervention arm: active drug 2.4mg/kg (n=35)
- High Dose intervention arm: active drug 4.8mg/kg (n=35)

The trial will be divided into two stages. The first stage will enroll patients into the Placebo (n=17) and Low Dose intervention arms (n=35), following which an interim analysis will be performed. The analysis will be limited to an analysis of safety data between the two groups. Provided there are no issues regarding safety or toxicity, the study will continue with the second phase enrolling patients into the high dose intervention arm (n=35) or placebo (n=18).

Each subject will be dosed and then remain in the study for 28 days or until they are discharged. There will be a 90-day follow-up though this will be conducted using data obtained via the NHS spine services (Health and Social Care Information Centre).

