13.5 Patient Allocation

13.5.1 Randomisation Method

A simple randomisation method will be used as detailed below:

- First stage: subjects will be randomised to Low dose active or placebo on a 2:1 ratio.
- Second stage: subjects will be randomised to High dose active or placebo on a 2:1 ratio.

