19.8 Adjusted analysis

The main analysis will be performed on unadjusted data. Continuous variables will be tested for normality and appropriate tests of comparison will be chosen accordingly.

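### The 78% power for each dose rests on pooling placebo across two sequential stages with no stage effect, an assumption section 19.1 does not state; with concurrent placebo it is about 62% and 63%

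*Protocol*

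**What the plan says.** Section 19.1 of the Protocol gives two power statements. For both doses together, "if Artesunate leads to a clinically relevant 2-point reduction in 48-hour SOFA score, this study will have a power of 80" per cent, with 70 active and 35 control patients in an unpaired t-test. For each dose, "We shall also perform two one-sided t-tests on each of the two intervention arm does levels against the placebo where 35 patients in each arm". The power given for that second calculation is 78%, again for a 2-point difference with alpha 0.05 and SD 3.43.

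Section 11.6 lists three arms of 35 but fills them in sequence: "The first stage will enroll patients into the Placebo (n=17) and Low Dose intervention arms (n=35", then a safety review, then 35 high-dose and 18 placebo patients. Section 13.5.1 confirms that each stage is randomised separately; for the later one, "Second stage: subjects will be randomised to High dose active or placebo on a 2:1 ratio". No patient can be allocated between the two doses.

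Placebo follows the stage's dose. Section 5.0 says of the control group: "Subjects will be receiving placebo at the same dose as treatment groups 1 or 2 respectively".

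Section 19.8 states: "The main analysis will be performed on unadjusted data". Section 19.5 plans standard two-group tests. Neither mentions stage.

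Among the reasons for the design, section 9.3 wants to learn "whether an increased dose of 4.8mg/kg Artesunate is more efficacious than 2.4mg/kg".

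**The concern.** Randomisation protects a comparison between patients who could have been allocated to either arm. Here that means low dose against 17 placebo patients and high dose against 18. The 35 v 35 test brings in the other stage's placebo patients, so about half of each control group is non-concurrent.

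Section 19.2 plans 24 months of recruitment. If case mix or care shifts between the stages, an unadjusted test with pooled placebo reads part of the shift as a drug effect, and in opposite directions for the two doses. A fall in SOFA over time would flatter high dose and penalise low dose, which looks like a dose response. Section 19.1 uses these results to decide whether a phase 2b trial is justified and how to design it, so both the error rate and the stated power matter.

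**Working it through.** **Inputs.** Difference 2 points, SD 3.43 and alpha 0.05 (section 19.1); 35 low dose with 17 placebo, then 35 high dose with 18 placebo (section 11.6). I take the planned counts as met.

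**Formula.** Standard error SE = 3.43 × √(1/n₁ + 1/n₂); noncentrality = 2/SE; power from the noncentral t with n₁ + n₂ − 2 degrees of freedom.

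**Step 1: the Protocol's own figures.**

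| Comparison | SE | 2/SE | Power, one-sided 0.05 | Power, two-sided 0.05 |
|---|---|---|---|---|
| 70 v 35 | 0.710 | 2.817 | 87.6% | 79.7% |
| 35 v 35 | 0.820 | 2.439 | 77.9% | 67.2% |

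The 78% reproduces only one-sided and the 80% only two-sided. Section 19.1 states no sidedness for the 80%; two-sided is inferred from the match.

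**Step 2: concurrent placebo only.**

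| Comparison | SE | 2/SE | Power, one-sided 0.05 | Power, two-sided 0.05 |
|---|---|---|---|---|
| Low dose, 35 v 17 | 1.014 | 1.972 | 61.8% | 49.0% |
| High dose, 35 v 18 | 0.995 | 2.010 | 63.3% | 50.5% |

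**Step 3: bias from pooling.** Let SOFA fall by D points between stages, for reasons unrelated to treatment. The pooled placebo mean falls by (18/35)D. High dose falls by D, so it gains D − (18/35)D = (17/35)D. Low dose does not fall, so it loses (18/35)D. D is an assumption throughout, because the Protocol gives no value. Type I error is the one-sided 35 v 35 test with noncentrality bias/0.820, ignoring the small extra spread that drift adds within the pooled placebo group.

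| Assumed fall D | Bias for high dose | Bias against low dose | Type I error, high dose | Type I error, low dose |
|---|---|---|---|---|
| 0.25 | 0.12 | 0.13 | 6.7% | 3.6% |
| 0.5 | 0.24 | 0.26 | 8.8% | 2.5% |
| 1 | 0.49 | 0.51 | 14.5% | 1.2% |
| 2 | 0.97 | 1.03 | 31.9% | 0.2% |

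A rise in SOFA would reverse the roles of the two doses.

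**Step 4: the 70 v 35 comparison.** Each stage contributes information n₁n₂/(n₁ + n₂): 35 × 17/52 = 11.44 and 35 × 18/53 = 11.89. The stratified SE is 3.43/√(11.44 + 11.89) = 0.710, the same as unstratified. Drift hardly touches this comparison even unadjusted: half of the active patients (35/70) and 18/35 = 0.514 of the placebo patients come from the second stage, so the bias is about 0.014D.

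**Step 5: high against low dose.** A direct contrast carries the whole of D. The difference of the two within-stage effects removes an additive shift, with SE = 3.43 × √(2/35 + 1/17 + 1/18) = 1.42 and a 95% half-width of 1.96 × 1.42 = 2.8 points.

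**Step 6: two dose tests.** The chance of at least one false positive across two one-sided 0.05 tests is 8.8% with a shared placebo group of 35 (bivariate normal, correlation 0.5) and 1 − 0.95² = 9.75% with separate placebo groups.

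**The case against.** Several replies have force.

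- **The 78% is not a miscalculation.** A reader might infer an arithmetic error. There is none: the figure is correct for the 35 v 35 test that section 19.1 describes. What is missing is the condition under which it holds.
- **Multiplicity.** A reader might infer that two tests at 0.05 breach the stated alpha. They do not. A second test changes neither the power nor the alpha of the first, and section 19.1 claims no familywise control. This is a phase 2a trial looking for an early efficacy signal. The 8.8% to 9.75% is worth a sentence, no more.
- **Drift may be small.** This is one site with one set of entry criteria, and nothing in the Protocol suggests a particular size or direction. That stands, and is why a range is shown for both doses. It does not supply the missing assumption.
- **High v low.** A reader might infer a planned but confounded test. There is none. Sequential enrolment is a deliberate safety gate, and the question appears only in the rationale, not among the objectives, the endpoints or the analyses in section 19. The wording of that one aim goes further than the design can.
- **Placebo volume.** It differs by stage, but the buffer is the same, and the Protocol offers no evidence that volume affects SOFA. It adds little.
- **Remedy.** Making the pooled 70 v 35 test the sole primary would carry a price. If only the high dose worked, by 2 points, the average effect would be 1 point and two-sided power about 29%. Nothing here requires that change.

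**Conclusion.** The concern holds in limited form. Section 19.1's 78% is conditional on pooling placebo across stages with no stage effect. The Protocol neither states that condition nor plans a main analysis that protects against its failure. The randomised evidence for each dose has about 62% and 63% power at the Protocol's own difference, SD and one-sided alpha, some 15 to 16 points lower. The type I error figures depend wholly on an assumed drift: at 0.5 points they are 8.8% and 2.5%, at 1 point 14.5% and 1.2%, for high and low dose respectively.

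The documents do not support the reading that drift is expected or that the trial's overall comparison is compromised: the 70 v 35 test is almost unaffected. This should be fixed, but it does not invalidate the design.

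**What to change.** 1. **Sections 19.5 and 19.8:** analyse by stage. Stratify the 70 v 35 comparison by stage, and compare each dose with its own stage's placebo. Keep the pooled-placebo dose comparison as a sensitivity analysis, with its no-stage-effect assumption written down.
2. **Section 19.1:** restate the dose-level power as about 62% (35 v 17) and 63% (35 v 18), one-sided. Say that the 80% is two-sided and the 78% one-sided. Either give the 8.8% to 9.75% chance of at least one false positive or call the dose tests exploratory.
3. **Section 9.3:** describe high v low as a non-randomised comparison. If an estimate is wanted, use the difference of the two within-stage effects, with its interval of about ±2.8 points.

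**Cost.** No extra patients, and no loss of precision for the 70 v 35 comparison. The stated dose-level power becomes less favourable. If there is in truth no drift, the within-stage dose estimates are less precise than the pooled ones (SE 1.014 and 0.995 against 0.820); the sensitivity analysis still shows the pooled result.
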